Study Title:

Assessment of hepatic glucose and fat
regulation in overweight adolescent girls
(APPLE Study)

Protocol Version Date: 11/26/2018

NCT02157974

COMIRB Protocol

COLORADO MULTIPLE INSTITUTIONAL REVIEW BOARD
[name] [contact] [contact]

Project Title: Assessment of hepatic glucose and fat regulation in overweight adolescent girls

Version Date: November 26th 2018

Principal Investigator: [name] [name], PhD
Mentor: [name], MS

I. Hypotheses and Specific Aims:

HYPOTHESIS:

Obese girls with PCOS, when compared to obese controls, will have hepatic and adipose insulin resistance (IR) that is not overcome with endogenous insulin secretion following an oral glucose (OG) load. IR will be worse in girls taking oral contraceptives, and improved in girls taking metformin. Hepatic IR and fat will relate to a failure to suppress hepatic gluconeogenesis and utilize carbohydrates during feeding.

Specific Aims:

Aim 1: Optimize novel minimally-invasive physiologic methods to study liver and adipose IR.

Rationale: Our preliminary pediatric PCOS data show high rates of NAFLD, altered interactions between hepatic and adipose IR during IV studies, and abnormalities during an OG load. A single less invasive protocol to synthesize these findings is needed, and this is a novel approach.

Methods: 1) Optimize a combined oral glucose and stable isotope tracer model to assess hepatic and adipose IR, while simultaneously accounting for post-prandial hormone changes. This aim will be accomplished with completion of the first 15 subjects, who may or may not have PCOS.

Aim 1A: Develop a mathematical model to describe dynamics of glucose and glycerol during an OG and quantify key aspects of liver & adipose metabolism

Rationale: Tissue specific IR is detectable following an OG that includes stable isotope tracers, but mathematical modeling is required to correctly interpret data collected before and after an OG load.

Methods: In the initial 6 subjects we will 1) Develop a differential equations-based mathematical model of glucose and glycerol dynamics and fit to data computed from stable isotope tracer data. 2) Analyze model to characterize tissue specific IR in PCOS subjects. 3) Develop a model of glucose passage through the gastrointestinal tract to assess glucose absorption in PCOS subjects.

Aim 1B: Compare the OG glucose and glycerol rates of appearance to hyperinsulinemic euglycemic rates of appearance

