Fitting Ra: Using computed data points, glycerol and glucose R_a will be fitted with an appropriate model. In control subjects, R_a typically shows 3 phases in OGTT⁶⁰. Cubic polynomial, piecewise-linear, spline, and dynamic models have been used for fitting R_a in previous work^{61,62}. In a comparison of different models, the choice of model form did not significantly impact the resulting estimates of insulin sensitivity or glucose R_a . Given the expected 3 phase form of R_a , we will assume a cubic polynomial model; we will validate estimates obtained with the cubic polynomial model by computing comparable estimates using at least one other model form. In previous work comparing different models for R_a (piecewise-linear, cubic polynomial, dynamic), results have been relatively unaffected by choice of model. If we find that this is not the case for our data, then we would certainly consider the advantages of adopting a more complex approach, such as the state-space, for describing R_a .

Characterization of Liver and Adipose Metabolism through Model Analysis: The novel OMM* model will be used to measure insulin sensitivity and provide a quantitative characterization of glucose R_a in the 5 PCOS subjects, thereby providing insight into liver metabolism in these subjects. The following measures will be computed: mean of R_a ; area under the curve describing R_a during 4 hour period associated with OGTT; time to peak R_a suppression; and time to return to basal R_a post glucose load. A similar characterization of glycerol R_a in the 5 PCOS subjects will be computed using the novel OMM* glycerol model, thereby providing insight into adipose

metabolism in these subjects. In addition, the glucose and glycerol Ra suppression associated with OGTT will be compared to those already collected from hyper-insulinemic euglycemic clamp glycerol and glucose Ra suppression from an identical subject population to identify similarities and differences associated with protocol.

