Proposed Model of Glucose Absorption: A key advantage of OGTT over IV glucose delivery is the physiologic aspect of oral administration. When glucose is ingested, the physiologic pathway through the gastrointestinal tract contributes to the glucose rate of appearance in plasma. Although gastric emptying of liquids occurs exponentially in control subjects, there is evidence that gastric emptying may be delayed in certain populations, thereby impacting glucose absorption⁶³⁻⁶⁵. In order to assess possible abnormalities in glucose absorption in PCOS, we will relate a model that describes mechanisms of glucose transit through the gastrointestinal tract⁶⁰ to Ra data computed for PCOS subjects. The three-compartment model for glucose transit through the stomach and upper small intestine is described by the following system of differential equations:

$$\begin{aligned}\frac{dq_{sto1}}{dt} &= -k_{21}q_{sto1} + D\delta \\ \frac{dq_{sto2}}{dt} &= -k_{empt}(q_{sto})q_{sto2} + k_{21}q_{sto1} \\ \frac{dq_{gut}}{dt} &= -k_{abs}q_{gut} + k_{empt}(q_{sto})q_{sto2}\end{aligned}$$

where q_{sto1} and q_{sto2} are the amounts of glucose in the stomach (solid and liquid phase, respectively); δ is the impulse function associated with OGTT glucose delivery; D is the amount of ingested glucose; q_{gut} is the glucose mass in the intestine; k_{21} is the rate of grinding; and k_{abs} is the rate constant of intestinal absorption. The rate of gastric emptying, $k_{empt}(q_{sto})$, is a nonlinear function of the total amount of glucose in the stomach: $q_{sto}=q_{sto1}+q_{sto2}$. Then we compute $Ra(t) = f K_{abs} q_{gut}(t)$ where f is the fraction of intestinal absorption appearing in plasma. Model parameters will be determined by fitting to Ra and tracer data. Since model parameters reflect specific physiologic processes, they will provide additional insight into the mechanisms underlying abnormalities of glucose Ra in PCOS subjects.

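### The glucose-absorption model asks whether absorption is abnormal in PCOS but plans no control fit, and its printed Ra equation lacks the body-weight term that its data carry

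*Combined protocol and SAP*

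**What the plan says.** Under Proposed Model of Glucose Absorption (section VII), the purpose is stated as "In order to assess possible abnormalities in glucose absorption in PCOS", and the model is related "to Ra data computed for PCOS subjects". Aim 1A (section I) words the task the same way: "Develop a model of glucose passage through the gastrointestinal tract to assess glucose absorption in PCOS subjects". The characterization section just before it is also confined to PCOS: its measures are computed "in the 5 PCOS subjects, thereby providing insight into liver metabolism in these subjects". Controls enter the absorption section once, in a background remark: "Although gastric emptying of liquids occurs exponentially in control subjects".

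The model passes glucose through two stomach compartments and one gut compartment. The dose is described by "D is the amount of ingested glucose", and the gut content qgut is defined as a mass. The output is Ra(t) = f × Kabs × qgut(t), "where f is the fraction of intestinal absorption appearing in plasma". Parameters are to be obtained by fitting to Ra and tracer data. Under Proposed Isotope Tracer Calculations, Ra is defined in mg/kg/min with a glucose distribution volume of 180 ml/kg. Total Ra is there split into an exogenous part (Ra,EXO) and an endogenous part.

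**The concern.** There are two separate points.

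**Reference.** Whether absorption is abnormal in PCOS is a comparative question. A value of kabs, kempt or f estimated in PCOS girls shows nothing unusual until it is set against values from comparable girls without PCOS. The plan names no such fit, no contrast and no published reference values.

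**Units.** The model output and the data it is fitted to are on different scales, and the factor between them is body weight. The section offers its parameters as reflecting particular physiological processes. If the equation is fitted as printed, f would reflect body weight as well as absorption, and two girls who absorb identically would receive different values.

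What is at stake is the interpretation of an Aim 1A deliverable.

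**Working it through.** The documents give no sample size, power or numerical result for this model, so there is no figure to reproduce.

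**Reference group**

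- Named for the fit: PCOS subjects, in Aim 1A and in the absorption section.
- Control data: section III.B plans 20 obese controls. The procedure table in III.C lists 20 obese girls for glucose and glycerol tracers, and section IV says that every subject has the tracer OGTT.
- Planned comparison: the Overall Project Statistical Plan has a PCOS–control t test or Mann-Whitney test, set out with the primary outcome. It does not mention kabs, kempt or f.

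The control data will therefore exist, but no section assigns them to this model.

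**Units**

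1. D is an amount (mg). The drink holds a fixed 75 g of glucose, so D = 75,000 mg. The 40 mg/kg oral tracer adds 40 × 38 = 1,520 mg to 40 × 136.1 = 5,444 mg, too little to change the result.
2. qgut is a mass (mg), Kabs is per minute and f has no unit. So f × Kabs × qgut is in mg/min, whereas the Ra data are in mg/kg/min.
3. Mass balance: over the whole absorption period, the integral of Kabs × qgut equals D. The integral of the printed output is therefore f × D. The integral of exogenous Ra per kg is f(true) × D / BW, where BW is body weight.
4. Equating the two gives f(fitted) = f(true) / BW.
5. Because f only multiplies the curve, the same rate constants with f divided by BW reproduce the per-kg curve exactly. The weight factor goes into f alone.

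Permitted weights: a floor of 38 kg (III.D, Blood Sampling), an exclusion above 300 lb = 136.1 kg (Exclusion Criteria), and an MRI limit of 275 lb = 124.7 kg (III.D, MRI). The 60 and 90 kg rows are illustrative. With f(true) = 0.9 assumed in every girl:

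| Weight (kg) | Fitted f, equation as printed | Fitted f × weight | Fitted f, output divided by weight |
|---|---|---|---|
| 38 | 0.0237 | 0.900 | 0.900 |
| 60 | 0.0150 | 0.900 | 0.900 |
| 90 | 0.0100 | 0.900 | 0.900 |
| 124.7 | 0.0072 | 0.900 | 0.900 |
| 136.1 | 0.0066 | 0.900 | 0.900 |

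These values come from solving and refitting the three-compartment system to noise-free Ra every 15 min for 6 h. The rate values were assumed: k21 = 0.05 (held fixed), kabs = 0.04, and kempt between 0.01 and 0.05 per min. The fit recovered kabs and the kempt parameters unchanged at every weight.

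Spread in f with identical absorption: 136.1 / 38 = 3.58-fold, or 124.7 / 38 = 3.28-fold at the MRI limit. For a modest gap of 100 against 90 kg, 90/100 − 1 = −10%. None of these ratios depends on the assumed 0.9.

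**The case against.** **On units.** The section prints no units for D, qgut or its own Ra, and section VII leaves per-kg scaling implicit elsewhere: the infusion rate in the Steele equation is unlabelled although the infusions are dosed per kg. If D and qgut were meant per kg, the equation would be consistent. That reading is possible, but the documents state it nowhere. The printed definitions are an amount and a mass, and the drink is not scaled to weight. The plan should state which is meant.

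It is also fair that a fitted fraction near 0.01 would probably be noticed, and that multiplying by body weight restores it. The section's stated motive is delayed gastric emptying, which is carried by the rate constants, and these are not distorted. A reader might infer that every parameter of the model is compromised. The check above shows that, with f free, only f is. Distortion of the rate constants, or lack of fit, would arise only if f were held fixed, and the plan says parameters are fitted.

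**On the reference group.** The word only does not appear in the text. Aim 1A is method development in the first 6 subjects, the first 15 may or may not have PCOS, and section IV reviews early data from both groups. The model is taken from published work and control emptying is described. A reader might infer that the study has no controls, or that no parameter could ever be called abnormal. The documents do not support either: controls have the same test, and whether the cited model paper gives usable normal values cannot be judged from the protocol. What stands is narrower: the analysis as written names PCOS subjects alone and specifies no control fit, contrast or external reference.

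**Conclusion.** Both points hold in limited form.

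The absorption analysis poses a comparative question without planning the comparison, although the control data will be collected. That there is no control fit is inferred from the absence of one in every relevant section; it is not an explicit exclusion.

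Read literally, the output equation is off by a factor of body weight, so fitted f equals the true fraction divided by weight. This assumes that D is in mg, Ra is in mg/kg/min, f is free and the fitted series is exogenous Ra. The last is itself unstated, since the section refers simply to Ra and the Steele Ra is total Ra.

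The 3.3- to 3.6-fold spread joins eligibility extremes. A reader might take it as the variation to expect among enrolled girls, but the documents give no weight distribution and the spread in practice will be smaller. If the groups are of similar weight, the error mainly adds scatter to f; if they differ, it biases the contrast in f by the ratio of their weights.

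Nor should the point be read as touching the main results. The primary outcome is the insulin concentration that halves glucose Ra, and neither it nor any listed secondary outcome uses f, kabs or kempt. The correction is worth making, at modest priority.

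**What to change.** 1. Fit the same absorption model to the obese controls who have tracer OGTT data. Specify a PCOS–control comparison of kabs, kempt and f, labelled exploratory, and state which PCOS girls enter it.
2. Write the output as Ra,EXO(t) = f × Kabs × qgut(t) / body weight, or keep the equation and express Ra in mg/min. State the units of D, qgut and Ra beside it.
3. State that the fitted target is the exogenous Ra already defined under Proposed Isotope Tracer Calculations.

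The cost is additional model fits on data the protocol already collects, one corrected equation and a few sentences of text. No new subjects, visits or samples are needed, and the primary analysis does not change.

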Known obstructive sleep apnea or treatment with CPAP will not be an exclusion criteria, however, those individuals already utilizing CPAP at home will be requested to bring it for admission and use it during the WatchPAT study, so that we capture their typical home sleep patterns.

III. Research Methods

A. Outcome Measure(s):

Primary Outcome Measure(s): Insulin concentration suppressing 50% glucose Ra (IC₅₀ glucose Ra) during OGTT.

Secondary Outcome Measure(s): Hepatic PME/ATP ratio change after OG load, Glycerol Ra during OGTT, Hepatic fat fraction from MRI, Rate of hepatic de novo lipogenesis.

Likely contributors to above measures: Lipid/glucose markers:(fasting C-peptide and lipid panel, HbA1c); hepatic markers:(c-reactive protein, glucagon, GLP-1 and leptin at baseline, 5 min and 30 min post glucose load to asses change with OG, adiponectin, AST, ALT, GGT), sex-steroids:(DHEAS, free and total testosterone, sex hormone binding globulin, progesterone, estradiol); Body size and composition: (BMI, waist/hip ratio, DEXA, hepatic visceral fat via MRI³⁸⁻⁴¹), Whole body fat oxidation at rest and following glucose ingestion as measured with a metabolic cart; metformin, OCP, Physical activity/ diet:(accelerometer, activity survey (3DPAR); Food frequency survey).Questionnaires for presence of obstructive sleep apnea. Questionnaires for perceived mental strengths and difficulty (note there is no assessment of suicidality on this tool). Obstructive Sleep Apnea, to be assessed with an overnight sleep study via WatchPAT

B. Description of Population to be Enrolled:

60 obese adolescent females with PCOS will be studied compared to 20 obese non-PCOS controls. This is number of studies needed to be completed statistically, thus more subjects may be enrolled, to allow for screen failures and dropouts. Total enrollment will be up to 105 subjects.

Ethnic Categories	Gender		
	Females	Males	Total
Hispanic or Latino	27	0	27
Not Hispanic or Latino	78	0	78
Ethnic Categories: Total of All Subjects	105	0	105
Racial Categories			
American Indian/Alaska Native	3	0	3
Asian	4	0	4
Native Hawaiian or Other Pacific Islander	3	0	3
Black or African American	20	0	20
White	75	0	75
Racial Categories: Total of All Subjects*	105	0	105

Inclusion Criteria:

- 1) Female
- 2) Ages 12-21

- 3) Sedentary- less than 3 hours of moderate (jogging, swimming etc) exercise a week.

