Differences between the two primary groups (PCOS, controls) will be assessed with a t test or for non-normally distributed data a non-parametric test such as Mann-Whitney U. Secondary outcomes include a Pearson correlation test of potentially related variables followed by targeted multiple regression to assess the relationship between hepatic IR or hepatic fat and adipose IR, hepatic gluconeogenesis, VAT, carbohydrate oxidation, androgens, metformin or OPC use and presence of OSA. As an exploratory analysis, the four groups will also be compared using an ANOVA. We recognized that we may not be powered for these analyses, but the data will be used as hypothesis generating for future studies.

The rate of hepatic De Novo lipogenesis is a secondary outcome. Based on our preliminary data that plasma markers of hepatic De Novo lipogenesis are 40% greater in those with fatty liver disease and the use of a high carbohydrate and fructose drink to increase the differences between groups, 10 subjects in each group will be needed to detect a difference in hepatic De Novo lipogenesis^{21,49,52}. The rate of hepatic De Novo lipogenesis will be correlated with measures of hepatic and adipose IR and MRI measures of NAFLD.

Non-Isotope OGTT calculations: The Matsuda model of IR will be used, and B-cell function [insulinogenic index ($\Delta I30/\Delta G30$) and ($\Delta C30/\Delta G30$) and disposition index ($1/IFasting \times \Delta I30/\Delta G30$) and ($1/CFasting \times \Delta C30/\Delta G30$) will be calculated^{40,53-55}.

Proposed Mathematical Model of Glucose and Glycerol Dynamics: The differential equations-based isotope labeled oral glucose minimal model (OMM*)⁵⁶ will be adapted to describe glucose and glycerol dynamics present in the collected data. In OMM*, the oral glucose minimal model (OMM) is modified to account for labeled glucose oral data obtained with the inclusion of a stable isotope tracer. This refinement allows an estimate of insulin sensitivity which is unique in that it accounts for both stimulation of adipose and muscle glucose uptake and inhibition of hepatic glucose release. In OMM*, glucose concentration G and insulin action on glucose disposal X are governed by the following equations:

$$\begin{aligned}\frac{dG}{dt} &= -[S_G^* + X^*] \cdot G + \frac{R_a(\alpha, t)}{V^*} \\ \frac{dX^*}{dt} &= -p_2^* \cdot X^* + p_3^* \cdot [I - I_b]\end{aligned}$$

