Analysis of the sleep study: Respiratory parameters of interest (defined below) include arousals, apneas, hypopneas, low oxygen saturation time (SaO2T), hypercapnia time (CO2>50), and oxygen saturation nadir (SaO2N). The arousal index (AI) is the number of arousals and awakenings measured by a shift of EEG signal to > alpha range for more than 3 seconds, divided by total sleep hours as previously defined(57). Apnea is defined as an absence of airflow for two or more breath cycles. Hypopnea is a visible decrease in airflow by nasal pressure signal (or by thermistor when pressure signal was unavailable) and either an EEG arousal or a drop in oxygen saturation of 3% or greater. Mixed apnea is an obstructive apnea combined with a central (absent effort) apnea. The AHI is comprised of the obstructive, mixed, and hypopnea events divided by total sleep hours; central apneas (seen in normal children)) are not included in the AHI. Intermittent hypoxemia, even brief episodes of mild drops from the normal baseline, is hypothesized to be a possible cause of neuropsychological dysfunction. SaO2T is the time in minutes with oxyhemoglobin saturation less than 95% measured by pulse oximetry in order to detect mild intermittent desaturation, (not seen in normal children. SaO2N is the nadir of oxyhemoglobin saturation. Hypercapnia time (CO2>50) is time in minutes with an end-tidal CO2 level greater than 50 mm Hg. Carbon dioxide levels are generally not measured in adult sleep laboratories. The AHI in normal non-snoring children has been determined to be less than 1.0, with little hypercapnia (sleep time with CO2 > 50 mm Hg, reported to be < 10-20%. There are no established diagnostic criteria for mild, moderate, or severe sleep apnea in children. OSA in adults is defined by the AHI: the number of apnea or hypopnea (partial obstruction) events per hour. However, continuous partial obstruction is underestimated by these criteria, and is considered significant by the Pediatric Sleep Program. Therefore, normal participants with evidence of continuous partial obstruction not meeting adult criteria for OSA, an AHI >1, or hypercapnia > 10% of sleep time will be excluded. For

this protocol, mild OSA is defined as AHI 1–4, moderate OSA as AHI 5–10, and severe OSA as AHI greater than 10.

All measures will be adjusted for OSA status (yes/no) and/or severity of AHI.

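### The sleep analysis section excludes undefined normal participants on sleep results, and its promise to adjust all measures for OSA conflicts with the covariate-free primary test

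*Combined protocol and SAP*

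**What the plan says.** Three places bear on who is analysed.

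- Section VII, Analysis of the sleep study, says that "normal participants with evidence of continuous partial obstruction not meeting adult criteria for OSA, an AHI >1, or hypercapnia > 10% of sleep time" are to be excluded. It does not say who the normal participants are, or whether they leave the study, an analysis or a reference group.
- The end of the Preliminary Studies says: "Known obstructive sleep apnea or treatment with CPAP will not be an exclusion criteria".
- The exclusion criteria in III.B and the discontinuation criteria in VI.C contain no sleep criterion.

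Three statements bear on how the comparison is made.

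- Section VII, Overall Project Statistical Plan: "Differences between the two primary groups (PCOS, controls) will be assessed with a t test", or with a test such as Mann-Whitney if the data are not normal. The power statement rests on the t test.
- The same section brings OSA in only through a secondary regression, whose list of terms ends with "metformin or OPC use and presence of OSA". PCOS group is not among the listed terms.
- The sleep analysis section closes with: "All measures will be adjusted for OSA status (yes/no) and/or severity of AHI".

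**The concern.** The Preliminary Studies name OSA as a possible confounder of the primary outcome, and the WatchPAT justification in III.D says it has to be accounted for when insulin resistance is measured. Two uncertainties follow.

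First, if normal participants means the non-PCOS girls, controls with OSA are removed while PCOS girls with OSA stay. The removal would usually come after the outcome data exist: the WatchPAT is worn the night before the tracer OGTT, and sleep studies are read within five business days. The rule also could not be applied evenly. Its hypercapnia criterion needs end-tidal CO2, which is listed only for polysomnography, and a girl may or may not have that study.

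Second, whoever is analysed, the plan allows both an unadjusted and an OSA-adjusted primary result. They answer different questions if OSA is partly a consequence of PCOS. The adjusted form is open too. The text allows a yes/no term, AHI severity or both, and it has no single cut: AHI 5 in the pilot data, mild OSA from AHI 1 in the sleep analysis, and 2 treated as normal at ages 12 to 17 in the follow-up section.

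**Working it through.** **The plan's own figure.** The power statement gives 86% for 13 controls and 32 PCOS girls, a difference of 35 and two-sided alpha 0.05. It states no SD. With SD 39, given for glucose IC50 in the method-development paragraph, two-sided t power is 76%; an SD of 34.2 returns 86%. Which SD was used cannot be decided, and nothing below turns on it.

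**Reading the exclusion sentence.**

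- *Normal as a sleep category.* Shortly before the exclusion, the section says that the "AHI in normal non-snoring children has been determined to be less than 1.0". Just after it, mild OSA is defined as starting at AHI 1. On this reading the sentence says who is not classed as having normal sleep, and no arm loses anyone.
- *Normal as non-PCOS.* This is possible, but elsewhere the comparison group is called obese, non-PCOS or controls.

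The text does not settle the choice.

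**Bias if controls only are removed and the unadjusted test is reported.** Inputs from the documents: 20 controls and 60 PCOS girls (III.B), SD 39 (VII). Assumed, because the documents give neither: an OSA effect on IC50 glucose Ra of 0.3 to 0.9 SD, and 30 to 50% of girls above the cut, equal in both arms. The 30 to 40% in the follow-up section concerns an AHI needing follow-up, not AHI above 1. The pilot split of 13 girls above AHI 5 and 13 below came from symptom-selected girls.

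Bias = share above the cut × effect in SD × 39.

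| Share | Controls left | Bias, 0.3 SD | Bias, 0.9 SD | False-positive rate, 0.3 / 0.9 SD |
|---|---|---|---|---|
| 30% | 14 | 0.30 × 0.3 × 39 = 3.5 | 0.30 × 0.9 × 39 = 10.5 | 6% / 12–13% |
| 40% | 12 | 0.40 × 0.3 × 39 = 4.7 | 0.40 × 0.9 × 39 = 14.0 | 6–7% / 16–17% |
| 50% | 10 | 0.50 × 0.3 × 39 = 5.9 | 0.50 × 0.9 × 39 = 17.6 | 7% / 21% |

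The rates come from simulating the two-sided t test with no true PCOS effect (20,000 runs per cell). With SD 34.2 the bias range is 0.09 × 34.2 = 3.1 to 0.45 × 34.2 = 15.4 units. The upper ends are generous, since a cut at AHI 1 counts mild OSA as OSA. In the same simulation, adding a yes/no OSA term at the same cut leaves bias within about 0.6 units and a rejection rate of about 4 to 6%, provided the OSA effect is additive.

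**Adjusted against unadjusted, nobody removed.** The two estimates differ by (difference in OSA share between arms) × effect × 39. Per 10 percentage points: 0.10 × 0.3 × 39 = 1.2 to 0.10 × 0.9 × 39 = 3.5 units, against a design difference of 35.

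**The case against.** The best defence of the exclusion sentence is that it defines normal sleep. It follows a passage on normal values, comes just before the OSA grading, and has no counterpart in the eligibility or discontinuation lists. The Preliminary Studies rule out only known OSA or CPAP as an exclusion, which leaves room for a narrow reconciliation. This stands as a plausible reading, so the documents do not show that controls will be dropped.

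A reader might also infer a serious loss of power. Against 60 PCOS girls, for a difference of 35 and SD 39, t-test power is 93% with 20 controls and 85%, 80% and 74% with 14, 12 and 10. Those figures leave out the OSA effect that produces the bias. When it is included, the rejection rate with exclusion is roughly 84 to 96% for shares of 30 to 50%, against 88 to 93% with all 20 controls kept. III.B also treats 20 as the number of controls to complete and allows extra enrolment, and the group table screens 20 to 30 controls. No power loss should be claimed.

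On adjustment, it can be said that the secondary regression of hepatic insulin resistance already contains OSA, so an adjusted analysis will sit beside the test. That is partly fair, but its listed terms do not include PCOS group, so as written it gives no adjusted PCOS-control difference. It can also be said that the adjustment sentence covers sleep measures only, given its heading. Adjusting sleep measures for OSA would make little sense, and the plan's concern is with the metabolic outcomes.

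**Conclusion.** The point holds in two parts of different strength. The firm part is the adjustment conflict, which needs no view on who the normal participants are: the plan allows two different primary estimates and does not say which counts. Their distance is unknown; under the assumed effects it is 1.2 to 3.5 units per 10 percentage points of imbalance in OSA.

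The conditional part is the exclusion sentence. It is undefined and unsupported by the eligibility text. Only if it is applied to controls alone, with the unadjusted test reported, does it bias the result toward a PCOS effect, by about 3.5 to 17.6 units with a false-positive rate of about 6 to 21%. Those ranges rest on an assumed OSA effect, an assumed share of controls above the cut, equal shares in both arms and SD 39. It would go too far to conclude that the trial will lose its controls with OSA. This should be fixed: the contradiction is plain, its numerical effect is uncertain, and the correction is cheap.

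**What to change.** 1. Reconcile the sleep analysis section with the WatchPAT text in the Preliminary Studies, the exclusion criteria and the discontinuation criteria. Delete the exclusion sentence from the analysis plan, or reword it as a definition of normal sleep. Either way, no participant is dropped from the PCOS-control comparison on sleep results, and one rule applies to both arms.
2. Reconcile the Overall Project Statistical Plan with the adjustment sentence. State in advance one OSA-adjusted model for IC50 glucose Ra, with group plus one prespecified AHI term and the AHI source (WatchPAT or polysomnography) recorded. Report it beside the unadjusted test, say which is primary, and note that OSA may be partly a consequence of PCOS, so the adjusted result may omit part of the PCOS effect.

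The AHI scale is the sponsor's choice. So is the handling of CPAP recordings, which arise because "those individuals already utilizing CPAP at home will be requested to bring it for admission and use it during the WatchPAT study".

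Cost: two sentences changed and one or two degrees of freedom, with no new measurement.
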